3.2 Patient Eligibility Criteria

Important note: The eligibility criteria listed below are interpreted literally and cannot be waived. All clinical and laboratory data required for determining eligibility of a patient enrolled on this trial must be available in the patient's medical/research record which will serve as the source document for verification at the time of audit.

All clinical and laboratory studies to determine eligibility must be performed within 7 days prior to enrollment unless otherwise indicated. Laboratory values used to assess eligibility must be no older than seven (7) days at the start of therapy. Laboratory tests need not be repeated if therapy starts within seven (7) days of obtaining labs to assess eligibility. If a post-enrollment lab value is outside the limits of eligibility, or laboratory values are > 7 days old, then the following laboratory evaluations must be re-checked within 48 hours prior to initiating therapy: CBC with differential, bilirubin, ALT (SGPT), and serum creatinine. If the recheck is outside the limits of eligibility, the patient may not receive protocol therapy and will be considered off protocol therapy.

Imaging studies, if applicable, must be obtained within 4 weeks prior to enrollment and start of protocol therapy (repeat the tumor imaging if necessary).

Echocardiogram, must be obtained within 8 weeks prior to enrollment and start of protocol therapy (repeat echocardiogram if necessary).

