3.2.3 Diagnosis

Histologically confirmed unresectable or metastatic translocation morphology renal cell carcinoma diagnosed using WHO-defined criteria. Patients may be newly diagnosed or have received prior cancer therapy.

3.2.3.1 Patients must have had histologic verification of the malignancy.

3.2.3.2 Patients must have measurable disease, documented by clinical, radiographic, or histologic criteria as defined by RECIST v1.1.

3.2.3.3 Patients must have a tumor showing the appropriate morphologic appearance, and either confirmed TFE3 nuclear protein expression by immunohistochemistry with appropriate positive and negative controls performed at a CLIA-certified laboratory, or evidence of TFE3 or TFEb translocation by either FISH or RT-PCR performed at a CLIA-certified laboratory. For TFE3 immunohistochemistry, any nuclear positivity in the presence of appropriate positive and negative controls should be considered as evidence of TFE3 immunohistochemical expression.

NOTE: If the institution is unable to perform these studies, unstained slides may be submitted to [name], who will perform TFE3 analysis at no charge. The slide will be returned to the referring institution for local evaluation, to be included in their institutional report. See [Section 14.1.2](#) for complete details.

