9.4 Endpoints and Evaluability

The primary endpoint is progression-free survival (PFS), which is defined as the time from randomization to the earliest occurrence of disease progression (as defined by modified RECIST criteria for immunotherapy, described in [Section 10](#)) or death due to any cause among patients who initiated protocol treatment. Patients not experiencing a PFS event by the time of a prospectively-planned interim or final analysis will be right-censored at the time of their most recent response/progression evaluation. Following the intent-to-treat principle, all patients who are randomized and confirmed to have tRCC by central pathology review will be evaluable for PFS. Patients randomized to Arm B prior to Amendment 2A, and patients who have a central path review confirming a diagnosis other than tRCC, or who never receive central path review per protocol, will be considered inevaluable for the primary endpoint comparison but included in study descriptive statistics.

The overall response rate (ORR) will be defined as the rate of complete or partial responses (assessed by imaging) among patients who initiated protocol therapy and completed at least one subsequent imaging assessment. Patients who are randomized to Arms A or C and are confirmed to have tRCC by central pathology review will be evaluable for ORR.

Overall survival (OS) will be calculated as the time from randomization to death due to any cause, with surviving patients being right-censored at their length of follow-up at the time of analysis. Patients who are randomized to Arms A or C and are confirmed to have tRCC by central pathology review will be evaluable for OS.

Note: For calculations of both PFS and ORR, any lesions resected during protocol therapy for reasons other than progression (as noted by sites or documented upon central surgical review) will not contribute toward response/progression assessments. Response/progression assessments are scheduled to take place after Cycles 2, 4, 6, 9, 12, and then every 4 cycles thereafter, after every cycle following any suspected pseudoprogression until the total tumor burden subsequently diminishes, or at any time clinical progression is suspected. Once in follow-up, patients without a documented PFS event will be evaluated according to the schedule in [Section 7.2](#). ORR and OS will be analyzed as a part of exploratory aim 1.3.1.

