If at the Week 12 assessment the total tumor burden has not yet diminished to $< 20\%$ increase from baseline or nadir, a patient may stay on protocol therapy so long as tumor shrinkage/stabilization continues to occur. If at any point after Week 12 the total tumor burden increases *and* is $\geq 20\%$ from baseline or nadir, this will be defined as progressive disease and the patient must be removed from protocol therapy.

Patients whose best response in the first 12 weeks is pseudoprogression, but who subsequently come off protocol therapy prior to any further assessment, will be considered as having progressive disease. This will include patients who are removed from protocol therapy due to resection of tumor lesions that are increasing in size (see [Section 13.1.8.2](#)).

Note: An increase in tumor size of $\geq 40\%$ at any time will be considered true progression and will result in removal from protocol therapy.

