10.2.2 Definitions

10.2.2.1 Evaluable for toxicity: All patients will be evaluable for toxicity from the time of their first treatment with axitinib, nivolumab, or the combination of axitinib and nivolumab.

10.2.2.2 Evaluable for objective response: Only those patients who have measurable disease present at baseline, have received at least one cycle of therapy, and have had their disease re-evaluated will be considered evaluable for response. These patients will have their response classified according to the definitions stated below. (Note: Patients who exhibit objective disease progression prior to the end of Cycle 1 will also be considered evaluable.)

10.2.2.3 Evaluable non-target disease response: Patients who have lesions present at baseline that are evaluable but do not meet the definitions of measurable disease, have received at least one cycle of therapy, and have had their disease re-evaluated will be considered evaluable for non-target disease. The response assessment is based on the presence, absence, or unequivocal progression of the lesions.

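### Section 9.4 defines ORR so that, read literally, patients never re-imaged leave the randomised comparison, and no rule counts them as non-responders

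*Combined protocol and SAP*

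**What the plan says.** Section 9.4 takes the ORR as the rate of "complete or partial responses (assessed by imaging) among patients who initiated protocol therapy and completed at least one subsequent imaging assessment". The sentence after it carries neither condition: "Patients who are randomized to Arms A or C and are confirmed to have tRCC by central pathology review will be evaluable for ORR".

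Section 10.2.2.2 sets a further test. Patients must have measurable disease at baseline, and must "have received at least one cycle of therapy, and have had their disease re-evaluated will be considered evaluable for response". One exception is written in: "Patients who exhibit objective disease progression prior to the end of Cycle 1 will also be considered evaluable". The measurable-disease condition removes nobody, because Section 3.2.3 already requires it at entry: "Patients must have measurable disease, documented by clinical, radiographic, or histologic criteria as defined by RECIST v1.1".

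Section 9.3 compares ORR formally between arms at the time of the final PFS analysis. The model is a stratified logistic regression, reported as an odds ratio for arm with a 70% confidence interval.

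For PFS, Section 9.4 also limits its definition to patients who began protocol treatment, and then adds: "Following the intent-to-treat principle, all patients who are randomized and confirmed to have tRCC by central pathology review will be evaluable for PFS".

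**The concern.** Starting therapy and being re-imaged both happen after randomisation. A patient who dies, withdraws or is lost before any scan cannot be recorded as a responder. Removing that patient raises the reported rate in the arm concerned and moves the odds ratio towards that arm. The same holds for a randomised patient who never starts, and Section 3.2 gives one route to that, a failed repeat of the laboratory tests: "If the recheck is outside the limits of eligibility, the patient may not receive protocol therapy and will be considered off protocol therapy".

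No section classifies these patients as non-responders. The best-response table in 10.2.5.3 has no row for target lesions that were never re-assessed, and the symptomatic-deterioration note beneath it is a reporting label rather than a response category. The plan does write such a rule for a neighbouring case, early pseudoprogression with nothing better recorded. Section 10.2.1 rules on it in these words: "but who subsequently come off protocol therapy prior to any further assessment, will be considered as having progressive disease".

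What is at stake is the ORR in each arm and the odds ratio between them. Two analysts could build different ORR datasets and each cite the protocol. At this sample size a denominator chosen after the data are seen would be hard to defend.

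**Working it through.** **1. The three wordings side by side**

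| Randomised, confirmed Arm A/C patient | 9.4 definition | 9.4 evaluability sentence | 10.2.2.2 |
|---|---|---|---|
| Never starts therapy | out | in | out |
| Starts, no later scan | out | in | out |
| Under one cycle, later scan without progression | in | in | out |
| Objective progression on a scan before end of Cycle 1 | in | in | in |

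The two sentences of 9.4 can be read together (the rate is taken among treated and re-imaged members of the evaluable set) or as two denominators. The text does not choose.

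**2. Inputs**

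The target is 28 patients (9.1), randomised 1:1 (9.2), so about 14 per arm. The first scheduled scan follows Cycle 2 (4.1), at about 8 weeks. The plan gives no expected ORR, no power for ORR and no count of patients without a scan, so there is no ORR figure to reproduce. The responder counts and losses below are assumptions.

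**3. How many might be lost through early death**

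Assume exponential survival with median m months. Eight weeks is 56/30.44 = 1.84 months. Expected deaths before then are 28 × (1 − 2^(−1.84/m)).

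- m = 18.2 and 25.5 (the range of nivolumab medians in 2.2.2, for RCC rather than tRCC): 1.9 and 1.4 patients.
- m = 12 and 36 (assumed wider range): 2.8 and 1.0 patients.

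This is an upper estimate of loss through death, since some of these patients would be scanned first. Withdrawals, losses and never-started patients come on top, and the documents give no number for them.

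**4. Effect on the rate in one arm**

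- 4 responders: 4/14 = 28.6%; one non-responder dropped, 4/13 = 30.8%; two dropped, 4/12 = 33.3%. The rise is 2.2 or 4.8 points.
- 6 responders: 6/14 = 42.9%; 6/13 = 46.2%; 6/12 = 50.0%. The rise is 3.3 or 7.1 points.

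**5. Effect on the odds ratio**

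Assume 6/14 responders in Arm A and 4/14 in Arm C, with every lost patient a non-responder. The odds ratio is unstratified, with a Wald 70% interval: exp(ln OR ± 1.036 × SE), where SE is the square root of the sum of the reciprocals of the four cells. With all counted, OR = (6/8)/(4/10) = 1.875, SE = √(1/6 + 1/8 + 1/4 + 1/10) = 0.801, interval 0.82 to 4.30.

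| Lost from A, C | Odds ratio | 70% CI |
|---|---|---|
| 0, 0 | 1.88 | 0.82–4.30 |
| 1, 0 | 2.14 | 0.92–4.97 |
| 0, 1 | 1.69 | 0.73–3.90 |
| 2, 0 | 2.50 | 1.06–5.89 |
| 1, 1 | 1.93 | 0.83–4.51 |
| 0, 2 | 1.50 | 0.64–3.50 |

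**6. How often the reading changes**

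In this illustration one loss never makes the interval exclude 1. Two or three losses do so only if all fall in Arm A: (2, 0) gives a lower limit of 1.06 and (3, 0) gives 1.25, while (2, 1) gives 0.95. If every patient is equally likely to be lost, the chance is (14 × 13)/(28 × 27) = 0.24 for two and 0.11 for three. Among the 8 + 10 non-responders only, it is 28/153 = 0.18 and 56/816 = 0.07.

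With an assumed 7/14 v 3/14, close to the RCC response rates in 2.2.3 (45–52%, nivolumab plus sunitinib or pazopanib) and 2.2.2 (20–25%, nivolumab alone), OR = 3.67 (1.53–8.78). The lower limit stays above 1 for every split of up to three losses; the lowest is 1.09, with three lost from Arm C.

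**The case against.** The strongest reply is that the plan already keeps this group small. Scans are required whenever progression is suspected and at end of therapy (4.1, 7.1, 16.2). Patients off therapy are followed until they meet the off-study criteria (8.1), with imaging from month 3 of follow-up (7.2), and 10.2.5.3 asks that progression be documented even after treatment stops. The 9.4 condition is any later scan, not an on-treatment scan, so a patient who stops early for toxicity can still meet it. Entry also requires a life expectancy of at least 8 weeks. This stands: what remains under 9.4 is death, withdrawal or loss before any scan, and never starting. The at-least-one-cycle test in 10.2.2.2 could drop a few more.

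It can also be said that a re-evaluated denominator is a declared choice for a non-primary endpoint. That would carry more weight if the next sentence of 9.4 did not declare a different set.

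A reader might infer that the plan protects PFS by intent-to-treat and withholds the same protection from ORR. The documents do not support so clean a contrast. The PFS definition carries the same limitation to patients who began treatment, followed by a sentence admitting all randomised, confirmed patients. The difference is that the PFS sentence names the intent-to-treat principle and the ORR sentence does not. The parallel even lends some support to reading the ORR evaluability sentence as the analysis population, which is why the exclusion is a literal reading and not a certainty.

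Finally, counting every unscanned patient as a non-responder would misclassify someone enrolled shortly before an event-driven cutoff and not yet due a scan. That is right, and the fix allows for it.

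**Conclusion.** The point holds as a defect of definition. Section 9.4 does not settle the ORR denominator, its definition read literally conditions a randomised comparison on events after randomisation, and no rule covers patients never re-imaged. It should be settled before the final analysis.

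The likely size is modest. One or two exclusions raise an arm's rate by about 2 to 5 points at 4/14 responders (3 to 7 at 6/14). In the 6/14 v 4/14 illustration they move the odds ratio from 1.88 to between 1.50 and 2.50. The usual effect is a shifted estimate, not a changed reading. These figures rest on assumed responder counts, assumed losses and an unstratified model.

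A reader might infer that the definition favours the combination arm. The documents do not support that: the direction depends on which arm loses more patients before a scan, and nothing in them says which. Nor does any decision rule depend on ORR. The design and decision rules rest on PFS, where the matching phrase needs reconciling with the intent-to-treat sentence, but that sentence already states the intended population.

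**What to change.** State in 9.4 that ORR is the proportion with CR or PR among all patients randomised to Arms A or C with centrally confirmed tRCC. Patients with no post-baseline imaging count as non-responders, except those still in follow-up and not yet due a first scan at the data cutoff, who are listed separately. Report the re-imaged set of 10.2.2.2 as a sensitivity analysis and say there that this is its role. In the PFS definition, reconcile the limitation to patients who began treatment with the intent-to-treat sentence that follows.

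A minor editorial point in the same place: 9.3 calls ORR and OS secondary, while 9.4 puts them under exploratory aim 1.3.1 and the only secondary aim (1.2.1) is toxicity. Make 9.3 and 9.4 agree.

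The cost is a rule of one or two sentences in 9.4, one phrase in the PFS definition, a line in 10.2.2.2 and one label, with no change to sample size or visit schedule. The downside is a slightly lower reported ORR.

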9.5 Monitoring Boundary for Dose-Limiting Toxicities

Definitions of DLTs provided in ADVL1315 (for axitinib related DLTs) and ADVL1412 (for PD1-targeting immune checkpoint DLTs) will be used ([Section 5.1](#)). DLTs in each arm will be monitored at least weekly to ensure there is no excess toxicity, specifically. No

more than 3 patients (in the first 10 patients treated) experiencing protocol-defined DLTs during the first cycle (4 weeks) of treatment, and no more than 30% of patients experiencing protocol-defined DLTs during the first cycle (4 weeks) of treatment thereafter. Excess toxicities in the combination arm will lead to temporary suspension of accrual so discontinuation or dose reduction may be considered via a formal amendment.

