4.1 Overview of Treatment Plan

Prior to Amendment 2A, the study was a randomized three-arm phase 2 study evaluating the clinical benefit of axitinib, nivolumab, and their use in combination for the treatment of tRCC.

As of Amendment 2A, Arm B (axitinib alone) is permanently closed to accrual, and prospective patients will be randomly assigned to one of the following arms:

Arm A: Axitinib + Nivolumab

Arm C: Nivolumab

As of Amendment 5A, patients who are initially randomized to Arm C (nivolumab alone) and experience progressive disease prior to Cycle 22 will be permitted to crossover to Arm A (axitinib + nivolumab). For patients who crossover to Arm A, they are to continue on their current nivolumab schedule and start axitinib as soon as it is made available. NOTE: Patients must use the NCI supplied drug. Commercially supplied axitinib is not allowed.

Axitinib will be administered at a starting dose of 5 mg PO BID for patients \geq 18 years of age, and at 2.4 mg/m²/dose (maximum of 5 mg/dose) PO BID for patients $<$ 18 years of age. See [Appendix IV](#) for axitinib dosing nomogram. Individual patient dose titration of axitinib (escalation from starting dose) is permitted on protocol therapy, at the discretion of the treating physician. Refer to [Section 4.3.3](#) or [4.4.3](#) for dose titration criteria.

Nivolumab will be given at either 240 mg IV every 2 weeks or 480 mg IV every 4 weeks for patients \geq 18 years of age, and at 3 mg/kg IV (maximum of 240 mg/dose) every 2 weeks for patients $<$ 18 years of age. Pre-medication is not required as infusion reactions are rare, but anaphylactic precautions should be observed during each infusion of nivolumab. If \geq Grade 2 infusion reaction occurs, the infusion should be stopped and supportive care given as per institutional guidelines. See [Section 5.3](#) for management and dose modification guidelines for infusion reactions. Investigators are advised to monitor for fever, chills, shakes, itching, rash, hypertension or hypotension, or difficulty breathing during and immediately after administration of nivolumab.

Combination therapy will be given with agents at full single agent doses as above.

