Each cycle of therapy will be 4 weeks. Tumor disease evaluation will occur after Cycles 2, 4, 6, 9, 12, and then every 4 cycles thereafter, or at any time clinical progression is suspected. If pseudoprogression is suspected (until any degree of response is observed), disease evaluation must occur after every cycle ([Section 10.2.1](#)). Absent disease

progression or unacceptable toxicity, patients may continue on protocol therapy for up to 2 years duration or completion of 26 cycles, whichever comes first. Disease evaluations (including imaging) will continue during follow-up according to the schedule outlined in [Section 7.2](#).

For patients who progress on Arm C prior to Cycle 22, cross-over to Arm A is permitted. Patients should resume Arm A therapy as soon as PD is identified. Nivolumab should continue uninterrupted according to the previously established schedule for that patient (either every 2 or 4 weeks). Axitinib should be added as soon as it becomes available from NCI and the patient has recovered from any relevant toxicity. Subsequent disease evaluations should occur as above timed from the first cycle of combination therapy. The first cycle of combination therapy after cross-over will be defined as the cycle for which > 14 days of axitinib is given, with Day 1 of Cycle 1 after cross-over defined as the day of first nivolumab dose during that cycle after axitinib is started or on the day axitinib is started if given concurrently. **NOTE:** The total protocol therapy received on AREN1721 (whether delivered on Arm A, Arm C, or Arm C+A) is not to exceed 26 cycles or 2 years, whichever comes first.

NOTE:

- Patients who have not had cytoreductive nephrectomy prior to trial enrollment but who elect to have cytoreductive nephrectomy during therapy may remain on protocol therapy.
- Cytoreductive therapy is not permitted in the first 12 weeks after starting protocol therapy.
- Axitinib must be held for 7 days before and after surgery. See [Section 13.1.2](#) for more details.

For COG Supportive Care Guidelines see:

<https://childrensoncologygroup.org/index.php/cog-supportive-care-guidelines>.

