5.0 DOSE MODIFICATIONS FOR TOXICITIES

5.1 Definitions of Dose-Limiting Toxicities (DLT)

DLT will be defined as any of the following events that are possibly, probably, or definitely attributable to protocol therapy.

NOTE: Dose-limiting hematological and non-hematological toxicities are defined differently. The Study Chair should be notified of any suspected or confirmed DLT.

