We will summarize the levels of analytes and tumor expression before and after treatment and evaluate the changes due to treatment after logarithmic transformation using the paired t-test. Analytes include myeloid derived stem cells (MDSC): CD45, CD11b, CD33, CD14, CD15, HLA-DR, viability, stain 1; Tregs: viability, CD45, CD4, CD3, CD24, FoxP3; CD8 T cells (CD45, CD8, CD3); CD8 phenotype and activation and exhaustion (CD69, CD38, PD1, CD244, TIM3). Tumor expression of PDL-1, PD1, CD3, CD4 and CD8 will be assessed using TFE RCC samples from the study and scored for intensity (0 – 3).

Exploratory Aim 1.3.4: To characterize the pharmacokinetics of axitinib when given in combination with nivolumab in pediatric patients with tRCC.

The population PK analysis will include all treated patients enrolled beyond Amendment 5A who have at least 1 concentration above the below limit of quantitation (BLQ) in patients treated with axitinib. Pooled PK analysis with another study is to explore the effect of age and body size on axitinib CL/F and Vd/F and make predictions on the dosing of axitinib in pediatric patients in different age groups. Exposure-response relationships will also be explored. The results will be reported separately in a population modeling analysis report. For the purposes of PK analysis, patients who receive crossover therapy will be reported both as a separate cohort and pooled with patients receiving combination therapy up front.

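### Should the combination-arm DLT boundary in Section 9.5 say how it treats Arm C patients who cross over and add axitinib?

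*Combined protocol and SAP*

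**What the plan says.** Section 9.5 sets the boundary. "DLTs in each arm will be monitored at least weekly", with a limit of no "more than 3 patients (in the first 10 patients treated) experiencing protocol-defined DLTs during the first cycle (4 weeks) of treatment" and a 30% limit, over the same first-cycle window, after the tenth patient. The consequence is tied to one arm: "Excess toxicities in the combination arm will lead to temporary suspension of accrual", so that an amendment can be considered. Crossover is not mentioned.

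Section 4.1 lets an Arm C patient who progresses before Cycle 22 move to Arm A. "The first cycle of combination therapy after cross-over will be defined as the cycle for which > 14 days of axitinib is given". That definition times later work-up: "Subsequent disease evaluations should occur as above timed from the first cycle of combination therapy". Sections 4.3.2, 15.1.2 and 16.2.1 use it for PK sampling and imaging. Section 4.3.3 keeps the earlier Arm C cycles in the total therapy count.

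Elsewhere the treatment of crossover is explicit. Under Section 9.3, outcomes after crossover stay out of the primary PFS comparison. Adverse events during crossover are analysed, with crossover shown as a third group beside the two arms. For PK, "patients who receive crossover therapy will be reported both as a separate cohort and pooled with patients receiving combination therapy up front".

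On reporting, Section 5.1 states: "The Study Chair should be notified of any suspected or confirmed DLT". Section 11.10 puts all DLTs into routine reporting. Section 12.2 sends unexpected frequencies of serious events to the DSMC, which may recommend modifying or ending the study.

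**The concern.** A patient who crosses over is newly exposed to the combination, but that patient's first cycle of treatment was nivolumab alone. Read strictly, a DLT that appears when axitinib is added falls outside the window in Section 9.5. Yet Section 4.1 says such patients move to Arm A, and Section 9.5 acts on the combination arm, so another reader could include them. Two careful statisticians could apply the boundary differently.

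Toxicity is the only secondary aim in Section 1.2, and Section 2.3 reports no data on this combination in children. If several crossover patients had DLTs, whether enrolment paused could depend on a reading chosen after the events were seen.

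**Working it through.** **What there is to reproduce.** Section 9.5 gives a rule but no operating characteristics. Its two stages agree: 3/10 = 30%.

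**Inputs.** From the documents: target accrual 28 (9.1), 1:1 allocation (9.2), hence 28/2 = 14 per arm; 22 PFS events and 14 months of further accrual (9.1); 28-day cycles and crossover only before Cycle 22 (Section 4). Assumed, because the documents give neither: 3 to 12 crossovers, and the DLT rates shown. If all 22 events occur with 14 patients per arm, at least 22 - 14 = 8 are in Arm C. Deaths, progression too late or too early for crossover, and refusals reduce the number who cross.

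**Step 1, first ten patients.** P(X >= 4) with X ~ Binomial(10, p) is 1.3%, 12.1%, 35.0% and 61.8% at p = 10%, 20%, 30% and 40%.

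**Step 2, Arm A alone.** Update f_k(x) = f_{k-1}(x)(1 - p) + f_{k-1}(x - 1)p patient by patient. Remove the mass where x > 3 (k up to 10) or x > 0.3k (k above 10), taking the 30% as cumulative. With 14 patients the removed total, the chance of ever triggering, is 3.4%, 25.3%, 57.9% and 83.1% at the same rates.

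**Step 3, can the reading change the decision?** Yes. With 3/14 = 21.4% in Arm A, DLTs in the first two crossovers give 4/15 = 26.7% and then 5/16 = 31.3%, over the limit if pooled. Under the strict reading the count stays 3/14. Two DLTs in two patients has probability 0.2 x 0.2 = 4% at a 20% rate and 0.3 x 0.3 = 9% at 30%.

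**Step 4, a second count pooling crossovers with Arm A** by first axitinib dose. The trigger is either count. Simulation, 300,000 replicates, Arm A order kept the same in both counts, 3 to 12 crossovers:

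| DLT rate, Arm A / crossover | Arm A count only | Crossovers after Arm A | Starts interleaved |
|---|---|---|---|
| 10% / 10% | 3.4% | 3.7-3.9% | 5-6% |
| 20% / 20% | 25% | 28-32% | 33-40% |
| 30% / 30% | 58% | 63-72% | 68-78% |
| 20% / 30% | 25% | 30-43% | 37-55% |

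Full interleaving is an extreme: crossover exists only from Amendment 5A and needs progression, and the first scheduled imaging is after Cycle 2. If crossovers start after seven Arm A patients, the 20% / 20% row gives 32-38%.

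At a true rate of 40% throughout, above the limit, Arm A alone triggers 83% of the time. Adding 4, 8 or 12 crossovers after Arm A gives 88%, 92% or 94%.

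**Step 5, pooling instead of the Arm A count.** At 40% in Arm A and 10% after crossover, interleaved, detection falls from 83% to 58-77%.

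**Step 6, does the consequence reach crossovers?** Crossover can follow up to 21 cycles: 21 x 28 = 588 days, about 19.3 months. Accrual is expected to take 14 months. A pause in enrolment may come after enrolment has ended.

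**Step 7, what separate reporting shows.** Take 3/14 in Arm A and 4/8 after crossover. Pooled, this is 7/22 = 32%, barely over the limit. Listed separately, crossover shows 50%.

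**The case for a change.** The strongest case for a change is that the plan settles crossover for PFS, adverse events and PK but not for the one rule with an automatic consequence. The third-group summary in Section 9.3 is made at the final analysis, so it does not replace ongoing monitoring. The Study Chair and DSMC routes carry no numeric limit. If crossover toxicity exceeds that in Arm A, the difference is not trivial: 25% against 30-43% in the 20% / 30% row. A sentence written beforehand costs little and prevents a choice made after the events.

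The silence stands, and so does the absence of a numeric limit for crossover starts. It is also true that the definition requiring more than 14 days of axitinib, if borrowed for DLT counting, could miss a patient who stops early. A team that tabulates these events would sensibly count from the first axitinib dose.

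The objection does not show that the boundary should include crossovers. They have progressed and have already received nivolumab, so pooling assumes a comparability that the documents do not establish, and Section 9.3 keeps them apart for toxicity. A sentence excluding them would meet the objection equally well, which makes this an unwritten policy rather than an error in the design.

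**Conclusion.** No change follows. Section 9.5 was not aligned with the crossover, but the study team can fill the gap sensibly from the rest of the plan. It can keep the boundary on patients who start on the combination, list crossover DLTs separately as Section 9.3 does for adverse events, and take any cluster to the DSMC under Section 12.2. These events are already notified and recorded, so no safety information is lost.

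A pooled second count is a trade-off. At a 20% DLT rate it adds 3 to 7 points to the chance of a trigger if crossovers follow Arm A (25% to 28-32%), and 8 to 15 if starts interleave (25% to 33-40%). At 40%, with crossovers after Arm A, it adds 5 to 11 points to a detection chance of 83%. Its consequence, a pause in enrolment, may miss the late crossovers it is meant to protect.

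These sizes rest on 14 Arm A patients, assumed crossover numbers and DLT rates, and a cumulative reading of the 30% limit. More than 14 may be treated, since the ceiling is 40 and toxicity is evaluable in everyone treated (10.2.2.1). The gain from pooling would be larger if crossover toxicity were well above that in Arm A, but a separate listing shows that case more clearly than a pooled rate.
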